5.2. Treatment Assignment

Subjects will be assigned to study treatment in accordance with the randomisation schedule.

Randomised treatment assignment will be done via the Interactive Voice Response System (IVRS), and randomisation will be implemented based on a sequestered fixed randomisation schedule. Study centre personnel will call the IVRS once a subject has met all prerequisites for randomization; the IVRS will assign treatment.

Blinded study centre personnel will receive a randomisation notification indicating the unique subject identifier (randomisation number) and the date and time of randomisation. Each randomisation number will be a unique identifier. Once a randomisation number has been assigned, the number will not be reused even if the subject withdraws before receiving any investigational product. Details of the treatment assignment process are contained in the SRM.

5.3. Blinding

This is a double-blind study, neither the subject nor the study physician will know which of the two treatments (albiglutide or placebo) the subject is receiving.

The investigator or treating physician may unblind a subject's treatment assignment **only in the case of an emergency or in the event of a serious medical condition, when knowledge of the study treatment is essential for the appropriate clinical management or welfare of the subject, as judged by the investigator**. Investigators have direct access to the subject's individual study treatment. It is preferred (but not mandatory) that the investigator first contacts the GSK Medical Monitor or appropriate GSK study personnel to discuss options **before** unblinding the subject's treatment assignment. If GSK study personnel are not contacted before the unblinding, the investigator must notify GSK as soon as possible after unblinding, but without revealing the treatment assignment of the unblinded subject, unless that information is important for the safety of subjects currently in the study. The date and reason for the unblinding must be fully documented in the appropriate data collection tool.

If a subject is unblinded by the investigator or treating physician then discontinuation of investigational product treatment for that subject will be at the discretion of the investigator. However, the subject should continue to be followed in the study (see Section 4.5).

GSK's Global Clinical Safety and Pharmacovigilance (GCSP) staff may unblind the treatment assignment for any subject with an SAE. If the SAE requires that an expedited regulatory report be sent to one or more regulatory agencies, a copy of the report, identifying the subject's treatment assignment, may be sent to clinical investigators in accordance with local regulations and/or GSK policy.

5.4. Product Accountability

In accordance with local regulatory requirements, the investigator, designated site staff, or head of the medical institution (where applicable) must document the amount of investigational product dispensed and/or administered to study subjects, the amount returned unused by study subjects, and the amount received from and returned to GSK, when applicable. Product accountability records must be maintained throughout the course of the study.

5.5. Treatment Compliance

Subjects will be instructed to return all unused and used injector pens at the visits specified in the Time and Events Table (Table 1) in order to perform drug accountability

and determine compliance. Subjects will be provided with a sharps container for the disposal of used pens. To comply with health and safety considerations there will be no count made of used pens; only returned unused pens will be counted. In addition, subjects will be provided with a pre-printed card at each dispensing visit to record the date of each dose. The card is to be returned at the next dispensing visit with the unused pens.

5.6. Concomitant Medications and Non-Drug Therapies

5.6.1. Permitted Medications and Non-Drug Therapies

The usual care provider will manage the subjects according to standard of care, following local prescribing information. Close adherence to professional society guidelines for standard of care therapies in type 2 diabetes and cardiovascular disease will be emphasized during study conduct. Standard of care is described in greater detail in Section 3.2.

Unless specified as a prohibited medication in Section 5.6.2, all concomitant medications should be considered permitted provided they are not contraindicated for the individual subject concerned.

Like other members of the class, albiglutide causes a delay in gastric emptying, and thereby has the potential to impact the absorption of concomitantly administered oral medications. This should be taken into account by investigators when prescribing concomitant medication.

It may be necessary to reduce the dose of concomitantly administered insulin secretagogues (such as SUs) or insulin to reduce the risk of hypoglycaemia when starting albiglutide.

All concomitant anti-hyperglycaemic medications (name of agent, total daily dose, start and stop dates) will be recorded in the eCRF at each visit. Concomitant cardiovascular medications taken during the study will also be recorded at each visit by class of agent. Additionally, all medications used within the 30 days prior to the onset and throughout the duration of an SAE, AE of special interest (Section 6.2.3), or an AE leading to discontinuation of investigational product will be recorded as individual agents, reason for use, together with start dates (and stop dates if applicable) and any changes since any previous AE.

5.6.2. Prohibited Medications and Non-Drug Therapies

Subjects may not take a GLP-1 receptor agonist (other than blinded investigational product), nor any investigational drug, during the study (and any follow-up period after discontinuing investigational product).

If a subject receives a prohibited medication, a protocol deviation will be recorded.

5.7. Treatment after the End of the Study

Following the final study visit subjects will be contacted by telephone 5 ± 1 weeks after last dose of study medication to assess any AEs ongoing since the last visit or newly emergent.

Subjects will be treated as deemed appropriate by the investigator following the end of the study. Investigational product will not be provided to subjects by GSK after the end of the study.

The half-life of albiglutide is approximately 5 days, and significant therapeutic concentrations can persist for 3 to 4 weeks after discontinuation. The choice of other medicinal products and dose selection should be considered accordingly, as adverse reactions may continue and efficacy may, at least partly, persist until albiglutide levels decline.

The investigator is responsible for ensuring that consideration has been given to the post-study care of the subject's medical condition whether or not GSK is providing specific post study treatment.

5.8. Treatment of Study Treatment Overdose

No data are available with regard to albiglutide overdose in humans. The highest recommended dose of albiglutide is 50 mg once weekly.

During clinical studies of subjects with type 2 diabetes, the highest dose of albiglutide administered was 100 mg subcutaneously every four weeks for 12 weeks. This dose was associated with an increased frequency of nausea, vomiting, and headache.

There is no specific antidote for overdose with albiglutide. In the event of a suspected overdose, the appropriate supportive clinical care should be instituted, as dictated by the subject's clinical status. Anticipated symptoms of an overdose may be severe nausea, vomiting or headache. A prolonged period of observation and treatment for these symptoms may be necessary, taking into account the half-life of albiglutide (5 days).

6. STUDY ASSESSMENTS AND PROCEDURES

The schedule of study assessments is shown in [Table 1](#) and [Table 2](#). Detailed procedures for each assessment are provided in the SRM.

Table 1 Time and Events Table

| Procedures ^{1,2} | Screening ³ | Randomization ³ /Baseline (can be same day as Screening Visit) | Study Drug Check Phone Call (4-6 wks post rand.) | Clinic Visit Month 4 ± 18 days then every 4 months ± 18 days throughout the study | Unscheduled dose adjustment visit (if warranted) | Final study clinic visit ⁴ (or early withdrawal) | Follow up Phone Call 5 ± 1 weeks after last IP dose |
|--|------------------------|--|--|---|---|--|--|
| Written informed consent | X | | | | | | |
| Review of Inc/excl criteria | X | X | | | | | |
| Demography & directed medical history | X | | | | | | |
| Assessment of MACE and micro-vascular events | | | | X | | X | |
| HbA1c | X ⁵ | | | X | | X | |
| Serum creatinine (eGFR) | X ⁵ | | | X (alternate visits) ² | | X | |
| Liver Function Tests (LFTs) ⁶ | | X | | X (alternate visits) ² | | X | |
| Record available information on most recent lipid assessment ⁷ | | X | | X (annually) | | X | |
| Genetic sampling ⁸ | | X | | | | | |
| Patient reported outcomes questionnaires ⁹ | | X ¹⁰ | | X (alternate visits) ² | | X | |
| Key concomitant non-diabetes medication | | X | | X | | X | X |
| Diabetes medication | | X | | X | | X | X |
| Study drug reminder | | | X | X | X | | |
| Physical examination ¹¹ | | X | | X (alternate visits) ² | | X | |
| SAEs, AEs of special interest, AEs leading to IP discontinuation | | X | X | X | X | X | X |
| Pregnancy test ¹² | X | X | | | | | |
| Study drug dispense/compliance ¹³ | | X | | X | X | X | |

- Subjects who discontinue investigational product should be handled as described in Section 4.4 and Section 4.5 and in Table 2.
- Assessments at month 8, 16, 24 etc. will include patient reported outcomes questionnaires, serum creatinine (eGFR), LFTs and physical examination. Those at months 4, 12, 20 etc do not.
- Screening and Randomisation can occur at the same visit if all eligibility information is available. If Screening and Randomisation occur at the same visit assessments should not be duplicated.
- Once it is projected that the target number of MACE events will have been collected and that the projected median duration of subject follow-up is at least 1.5 years, a 3 month window will be defined for conducting the final, face to face visit.
- HbA1c and creatinine assessed using local laboratories at Screening visit and measured no more than 6 months prior to randomisation. If HbA1c or creatinine have not been assessed in the previous 6 months assessments to be performed via a central laboratory and results available prior to randomization. The investigator has the discretion to repeat

- screening HbA1c, and/or creatinine, based on clinical rationale even if previously available local results meet the eligibility criteria to allow the investigator to accommodate the possibility of change between screening and randomisation.
6. Liver function tests: ALT, AST, alkaline phosphatase, bilirubin, GGT. Blood samples for LFTs at randomization must be collected prior to the first dose of investigational product.
 7. Lipid values (TC, LDLc, HDLc, Tg) to be recorded as available from routine clinical care at baseline and annually thereafter. If results are unavailable, lipids tests are not to be performed for the study.
 8. Informed consent for genetic research must be obtained before collecting a sample. This can be collected at any time after genetic consent has been obtained and randomisation has occurred.
 9. TRIM-D, EQ-5D and study specific questionnaire (details in Section 6.3).
 10. TRIM-D is not required for subjects whose diabetes is treated by diet and exercise alone at Baseline.
 11. See Section 6.2.7.
 12. Only applies to women of child bearing potential. At screening perform urine pregnancy test. If positive, send serum sample to the central laboratory for confirmation. At Randomisation perform a urine pregnancy test. If result is positive do not randomize the subject. If the urine pregnancy test is negative then the subject can be randomised. If Screening and Randomisation are to take place at the same visit then follow the instructions for Screening. See Section 6.2.6.
 13. Study drug dispensing not performed at final visit, compliance check not performed at Randomisation.

Table 2 Time and Events Table for Subjects Who Permanently Discontinue IP Prior to the End of the Study

| Procedures | Clinic visit as soon after permanent discontinuation of IP as possible | Phone Call 5 ± 1 week after last IP dose | Continue contact schedule established at randomisation 4 monthly ± 1 month. Telephone ^{1,2} | Continue contact schedule established at randomisation 4 monthly ± 1 month. Clinic visit ^{1,3} | Final study clinic visit ⁴ |
|---|--|--|--|---|---------------------------------------|
| Assessment of MACE and micro-vascular events | X | | X | X | X |
| HbA1c | X | | | X | X |
| Serum creatinine (eGFR) | X | | | X | X |
| Liver Function Tests (LFTs) ⁵ | X | | | X | X |
| Record available information on most recent lipid assessment ⁶ | X | | X (annually) | X (annually) | X |
| Patient reported outcomes questionnaire ⁷ | X | | | | |
| Key concomitant non-diabetes medication | X | X | X | X | X |
| Diabetes medication | X | X | X | X | X |
| Physical examination ⁸ | X | | | X | X |
| AEs leading to IP discontinuation | X | | | | |
| SAEs, AEs of special interest, | X | X | X | X | X |
| Study drug compliance | X | | | | |

1. After subjects permanently discontinue IP, follow-up should continue on the 4-monthly schedule established at randomisation.
2. Where a subject would have been scheduled to attend clinic at months 4, 12, 20, 28 etc after randomisation, a telephone contact will be performed instead (with assessments as shown above).
3. Where a subject would have been scheduled to attend clinic at months 8, 16, 24, 32 etc after randomisation, a clinic visit will be performed (with assessments as shown above). If a subject who has permanently discontinued IP is unable to attend clinic then they will be contacted by telephone instead and the telephone contact assessments will be performed.
4. Once it is projected that the target number of MACE events will have been collected and that the projected median duration of subject follow-up is at least 1.5 years, a 3 month window will be defined for conducting the final, face to face visit.
5. Liver function tests: ALT, AST, alkaline phosphatase, bilirubin, GGT.
6. Lipid values (TC, LDLc, HDLc, Tg) to be recorded as available from routine clinical care annually. If results are unavailable, lipids tests are not to be performed for the study.
7. TRIM-D, EQ-5D and study specific questionnaire (details in Section 6.3).
8. See Section 6.2.7.

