In a Phase 3 study of patients with varying degrees of renal impairment, in the albiglutide group, on-therapy GI AEs occurred with a higher incidence and higher event rate in subjects with moderate and severe renal impairment compared to those with mild renal impairment. Because these GI events may lead to dehydration and worsen renal function, worsening renal function will be closely evaluated as an AE of special interest, serum creatinine will be measured every 8 months, and subjects will discontinue IP if eGFR falls below 15 mL/min/1.73m². Subjects with known severe renal impairment are excluded from the study (see Section 4.4.4).

Drug Interactions. Like other members of the class, albiglutide causes a delay in gastric emptying, and thereby has the potential to impact the absorption of concomitantly administered oral medications. During the development programme, drug interactions studies were conducted with digoxin, warfarin, oral contraceptives, and simvastatin which demonstrated no clinically relevant PK or PD effects. Investigators will be advised to take the effect of albiglutide on gastric emptying into account when prescribing concomitant medication.

Pregnancy and Lactation. Studies in animals have shown reproductive toxicity. The potential risk for humans is unknown. It is not known if albiglutide is secreted into human milk during lactation. Given that albiglutide is an albumin-based protein therapeutic, it is likely to be present in human milk. Decreased body weight in offspring was observed in mice treated with albiglutide during gestation and lactation. Subjects who are breastfeeding, pregnant or planning a pregnancy during the course of the study are excluded. Additionally, all females of child-bearing potential must be taking adequate contraception during the study and have a negative pregnancy test prior to entry.

Placebo control. In subjects treated with placebo, symptoms and long-term risks of hyperglycaemia may not improve or may worsen. During the study, intensification of glucose-lowering treatments other than study drug will be allowed in both treatment arms with a treat-to-target approach. Albiglutide placebo injections may cause injection site reactions. Subjects will be advised when injecting into the same region to use a different injection site each week.

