4.2. Exclusion Criteria

Deviations from exclusion criteria are not allowed because they can potentially jeopardise the scientific integrity of the study, regulatory acceptability or subject safety. Therefore, adherence to the criteria as specified in the protocol is essential.

A subject will not be eligible for inclusion in this study if any of the following criteria apply:

1. eGFR calculated using MDRD formula $<30\text{mL}/\text{min}/1.73\text{m}^2$ (based on the most recent documented serum creatinine laboratory assessment measured no more than 6 months prior to randomization. Local laboratory creatinine values taken as part of usual care are permitted) or renal replacement therapy.
2. Use of a GLP-1 receptor agonist at Screening.
3. Severe gastroparesis requiring therapy within 6 months prior to Screening.
4. History of pancreatitis or considered clinically at significant risk of developing pancreatitis during the course of the study (e.g. due to symptomatic gallstones, excess alcohol use).
5. Personal or family history of medullary carcinoma of the thyroid or subject with MEN-2. Personal history of pancreatic neuroendocrine tumours. In the opinion of the investigator, the subject has a medical history which might affect his / her ability to remain in the study for its entire duration, or which might limit management, such as life expectancy of <5 years (e.g. due to active malignancy).
6. Subject has a medical history which in the opinion of the investigator might limit the individual's ability to take trial treatments for the duration of the study or to otherwise complete the study.
7. Breastfeeding, pregnancy, or planning a pregnancy during the course of the study. Pregnancy test will be required in women of child bearing potential. Women who have undergone a sterilisation procedure or who are clearly post-menopausal will not be required to undergo pregnancy testing. Women who have developed spontaneous secondary amenorrhoea of 12 months or more where post-menopausal status is in doubt, a blood sample where FSH $>40\text{MU}/\text{ml}$ and oestrodiol $<40\text{pg}/\text{mL}$ ($<140\text{pmol}/\text{L}$) are simultaneously measured will be considered confirmatory.
8. Known allergy to any GLP-1 receptor agonist or excipients of albiglutide.
9. Use of another investigational product within 30 days or according to local regulations, or currently enrolled in a study of an investigational device.

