6.2.6. Clinical Laboratory Assessments

All protocol required laboratory assessments must be conducted in accordance with the Laboratory Manual, and Protocol Time and Events Schedule (Table 1). Details for the preparation and shipment of samples will be provided by the laboratory and are detailed in the laboratory manual. Reference ranges for all central laboratory safety parameters will be provided to the site.

If additional non-protocol specified laboratory assessments result in a change in subject management or are considered clinically significant by the investigator (e.g., SAE or AE of special interest or dose modification) the results must be recorded in the CRF.

Refer to the SRM/laboratory manual for appropriate processing and handling of samples to avoid duplicate and/or additional blood draws.

The following laboratory assessments will be performed: serum creatinine, HbA1c, liver function tests [AST (SGOT), ALT (SGPT), alkaline phosphatase, bilirubin, GGT], and urine and serum β hCG pregnancy test (for women of child bearing potential). All study-required laboratory assessments will be performed by a central laboratory, with the exception of HbA1c and creatinine at Screening and urine pregnancy test at Screening/Randomization.

Screening HbA1c and serum creatinine

Screening HbA1c and serum creatinine values should be based on the most recent local laboratory values taken as part of usual care within the previous 6 months and the values entered into the eCRF. These assessments must have been performed at an accredited laboratory. HbA1c screening results must be either Diabetes Control and Complications Trial (DCCT) aligned or International Federation of Clinical Chemistry and Laboratory Medicine (IFCC) standardized. HbA1c screening results from point of care equipment are acceptable provided that the equipment is maintained by an accredited laboratory. If HbA1c or creatinine have not been assessed in the previous 6 months, laboratory assessments will be performed via the central laboratory to determine eligibility (if a local laboratory is used in error the results are acceptable for determining eligibility). The investigator has the discretion to repeat screening HbA1c, and/or creatinine, based on clinical rationale even if previously available local results meet the eligibility criteria to allow the investigator to accommodate the possibility of change between screening and randomisation.

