6.2.6.1. Estimated Glomerular Filtration Rate (eGFR)

Serum creatinine will be measured every 8 months by a central laboratory. It will be used to calculate eGFR using the MDRD formula [Levey, 2009], namely:

$$\text{eGFR (ml/min/1.73m}^2\text{)} = 175 \times (\text{serum creatinine})^{-1.154} \times (\text{Age})^{-0.203} \times (0.742 \text{ if female}) \times (1.212 \text{ if African American}).$$

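### No creatinine is scheduled at Randomisation, so the eGFR baseline can be a local value up to 6 months old, up to 14 months before the first scheduled central value

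*Protocol*

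**What the plan says.** In Table 1 of the current protocol (Amendment 3), serum creatinine is marked at Screening, at alternate 4-monthly visits and at the final visit. The Randomisation/Baseline cell is empty. Footnote 2 places the alternate-visit samples at months 8, 16, 24 and so on.

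On the entry value, footnote 5 says "HbA1c and creatinine assessed using local laboratories at Screening visit and measured no more than 6 months prior to randomisation". Exclusion criterion 1 in Section 4.2 agrees: "Local laboratory creatinine values taken as part of usual care are permitted". Section 6.2.6 sends study laboratory tests to the central laboratory "with the exception of HbA1c and creatinine at Screening" (and the urine pregnancy test). There are two partial safeguards. Footnote 5 adds "If HbA1c or creatinine have not been assessed in the previous 6 months assessments to be performed via a central laboratory", with results back before randomisation. It also says "The investigator has the discretion to repeat" the screening test on clinical grounds even when the local result qualifies, because values may change before randomisation.

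On follow-up, Section 6.2.6.1 states: "Serum creatinine will be measured every 8 months by a central laboratory".

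For liver tests the arrangement differs. They are marked at Randomisation, and footnote 6 says "Blood samples for LFTs at randomization must be collected prior to the first dose of investigational product".

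The endpoint is change in eGFR (Section 2), reported as change from baseline (Section 8.3.5). Section 4.4.4 treats the entry eGFR as the baseline. Section 3.4.1.2 says "worsening renal function will be closely evaluated as an AE of special interest, serum creatinine will be measured every 8 months".

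**The concern.** The protocol names a renal risk: gastrointestinal reactions may lead to dehydration and worsen renal function. Reading that risk from laboratory data needs a value from shortly before the first dose, measured like the later ones. The schedule secures this for the liver but not for the kidney, although blood is being drawn pre-dose anyway.

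Two things can then be mixed into on-study change: true decline between the usual-care sample and the first dose, and any difference between the local and central assays. Section 6.2.6 requires an accredited laboratory for both tests, but asks for assay standardisation only for HbA1c. At stake are the within-arm change from baseline in eGFR and the interpretation of a fall seen in one subject at month 8. A statistical analysis plan can choose which value counts as baseline, but it cannot supply a sample that was never taken.

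**Working it through.** **Inputs from the protocol.** Maximum age of the entry creatinine: 6 months (Section 4.2, Table 1 footnote 5). First scheduled on-study creatinine: month 8, window 18 days either side (Table 1). Creatinine exponent in the MDRD formula: -1.154 (Section 6.2.6.1). Planned subjects: 9400 randomised 1:1, so up to 4700 per arm (Section 3.1). The protocol gives no figure for the gap or for a laboratory difference, so there is no stated number to reproduce.

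**Gap between baseline and first scheduled follow-up value.**
- As written: up to 6 + 8 = 14 months. With the window, 18/30.44 = 0.59 month, giving 14.6 months. This is the maximum; the protocol gives no distribution of sample ages.
- With a central sample at Randomisation: 8 - 0.59 = 7.4 to 8 + 0.59 = 8.6 months, both values central.

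**Effect of a laboratory difference (assumed sizes).** If central creatinine differs from local by a fraction b, the eGFR ratio with no true change is (1 + b)^-1.154.

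| b | ratio | change at eGFR 75 | change at eGFR 30 |
|---|---|---|---|
| -10% | 1.129 | +9.7 | +3.9 |
| -5% | 1.061 | +4.6 | +1.8 |
| +5% | 0.945 | -4.1 | -1.6 |
| +10% | 0.896 | -7.8 | -3.1 |

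Units are mL/min/1.73m2.

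**Effect on the between-arm comparison (assumed SDs).** Take a within-subject SD of 8 per central value, and an extra SD of 5 to 8 when the baseline is local. For a simple change score:
- Both values central: sqrt(64 + 64) = 11.3.
- Local baseline: sqrt(128 + 25) = 12.4 to sqrt(128 + 64) = 13.9, a rise of 9% to 22%.
- 95% CI half-width for the difference between arms with 4700 each: 1.96 x 11.3 x sqrt(2/4700) = 0.46; 1.96 x 12.4 x sqrt(2/4700) = 0.50; 1.96 x 13.9 x sqrt(2/4700) = 0.56.

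The percentage rise in SD looks notable, but in absolute terms the loss is at most about 0.1 mL/min/1.73m2 of half-width. These lines treat every subject as having a local baseline, so they overstate the loss to the extent that some have a central one.

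**The case against.** The strongest case on the other side is that this is a deliberate design. Section 3.1 aims at little intervention beyond usual care, with usual-care screening values and same-day randomisation, and nothing in the text contradicts itself. The protocol also foresees drift before randomisation: it allows a repeat test, requires a central test where no recent value exists, and has the eligibility criteria reviewed again at Randomisation. That stands as mitigation. It does not close the gap, because the repeat is discretionary and the central test is conditional.

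Four stronger readings might be inferred, and the documents do not support them.

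- **That the treatment comparison is biased.** In a 1:1 double-blind trial, the age of the local value and the laboratory differences should balance between arms. The comparison loses some precision and nothing more.
- **That worsening renal function cannot be placed before or after the first dose.** It is an investigator-reported event with targeted eCRF pages (Sections 4.4.4 and 6.2.3), not a defined change from the screening value. Events are asked about at the 4 to 6 week call and at every 4-monthly visit. Clinically significant non-protocol results must be recorded (Section 6.2.6), and subjects who permanently stop investigational product early have a creatinine at that visit (Table 2). The eGFR threshold in Section 4.4.4 is absolute and does not use the baseline. The difficulty is confined to decline seen only in the laboratory values.
- **That every subject is dosed without a current value.** It can happen; the text does not make it the rule.
- **That HbA1c has the same problem.** Screening HbA1c must be DCCT-aligned or IFCC-standardised, and its first on-study value comes at month 4, so the nominal maximum gap is 6 + 4 = 10 months. The point does not carry over.

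**Conclusion.** The point holds for creatinine as a cheap improvement to the schedule. The gap of up to 14 months (14.6 with the window) and the possible change of laboratory follow from the protocol's own text and need no assumption. The sizes attached to a laboratory difference and to the SDs are illustrative, since the protocol gives neither. A shift in a within-arm mean from the laboratory change would also require local laboratories to differ from the central one in a common direction, which nothing here shows.

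The consequence is limited. MACE is untouched, and the between-arm eGFR contrast is unbiased and nearly as precise. What is weakened is the within-arm change from baseline and the reading of individual laboratory decline. That is worth correcting in a trial that makes worsening renal function an adverse event of special interest.

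**What to change.** In Table 1 and Section 6.2.6, add central-laboratory serum creatinine to the pre-dose LFT sample already drawn at Randomisation. State that this value is the baseline for change in eGFR and for reading worsening renal function, with the screening value used if it is missing. Eligibility continues to rest on the screening value, so same-day randomisation is kept.

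The cost is one analyte per subject, with no extra visit or venepuncture. Some results will return after the first dose; they fall under the existing provisions of Section 4.4.4, and no new clinical rule is proposed. The change helps only subjects not yet randomised.
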